Note 2: An indeterminate QuantiFERON-TB Gold test may be repeated once during screening. If the repeat test is positive or indeterminate, the participant is excluded.

- b) Hepatitis C, Hepatitis B, or HIV infection as demonstrated, by a positive blood screen for HCV antibody and confirmed by positive reflex HCV RNA test, hepatitis B surface antigen (HBsAg), hepatitis B core antibody (HBcAb), or HIV-1 and -2 antibody.
 - i) Participants who have been vaccinated for hepatitis B (hepatitis B surface antibody [HbsAb]-positive) are not excluded.

- ii) Indeterminate tests require negative reflex testing results, or they are exclusionary.
- iii) HCV history and documented 24-week sustained virologic response are permitted.
- c) History of congenital or acquired immunodeficiency
- d) Participants with any acute or chronic bacterial, fungal (except history of tinea pedis or ongoing onychomycosis will not be exclusionary) or viral infection, as well as any febrile illness within 14 days of screening
- e) Known active infection, or any major episode of infection requiring hospitalization or treatment with parenteral (IM or IV) antimicrobial agents (eg, antibiotics, antiviral, antifungal, or antiparasitic agents) within 2 weeks of the screening visit, and/or completion of oral antimicrobial agents within 2 weeks of randomization, and/or recurrence prior to randomization.
- f) Previous history of recurrent herpes zoster (more than 1 episode), disseminated herpes simplex before randomization or a history of disseminated/complicated herpes zoster infection (multidermatomal involvement, ophthalmic zoster, eczema herpeticum, central nervous system involvement, or postherpetic neuralgia)
- g) History of atypical/opportunistic infection (eg, pneumocystis, cytomegalovirus, invasive fungal infections, atypical mycobacteria, etc.).
- h) Presence of the following COVID-19-related exclusion criteria
 - i) Symptoms of COVID-19 at screening or randomization
 - ii) COVID-19 (either suspected or confirmed) within 12 weeks of screening, at screening, and/or Day 1.
 - iii) Known or suspected current sequelae of any sort following any prior episode of COVID-19.
 - iv) COVID-19 vaccination within 14 days of screening or participant has plans to receive a vaccination during his/her participation in the study.

3) AD-related Criteria

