- a) High likelihood - based on participant history, and investigator judgement – of requiring rescue therapy in < 4 weeks prior to randomization (see [Section 7.7.2](#))
- b) Evidence of acute flare between the Screening and Baseline/ Randomization (eg, doubling of the EASI score between Screening and Baseline, or worsening that requires administration of prohibited medications).
- c) Skin lesion(s) and/or pruritus due to conditions other than AD that would interfere with the study specified assessments.

4) Prior/Concomitant Therapy

- a) Treatment with anticoagulant or antiplatelet therapies, including aspirin for cardioprotection, within 2 weeks prior to randomization or during the study.

- b) AD-related prescription or over-the-counter skin barrier treatments (eg, Cerave, Epicerum, etc.) therapy within 2 weeks prior to randomization
- c) Any bleach baths within 2 weeks prior to randomization
- d) Monoamine oxidase inhibitors (eg, selegiline, phenelzine) within 2 weeks prior to randomization
- e) Use of strong or moderate inhibitors or inducers of CYP2C8 or CYP3A4 within the longer of 5 PK half-lives or 14 days prior to randomization (inhibitors), or within 3 weeks prior to randomization (inducers).
 - i) Please refer to [Table 7.7.1-1](#) for examples.
 - ii) Sponsor's Medical Monitor should be consulted for any uncertainties regarding CYP2C8 or CYP3A4 modulators.
- f) Phosphodiesterase-4 (PDE4) inhibitors within 3 weeks prior to randomization.
- g) Use of phototherapy (ie, UVB, UVA) within 4 weeks prior to randomization.
- h) Leukotriene inhibitor treatment within 4 weeks prior to randomization.
- i) Diquafosol or rebamipide therapy within 4 weeks prior to randomization.
- j) Systemic corticosteroid treatment within 4 weeks prior to randomization.
- k) Systemic immunosuppressive drugs (CsA, MMF, AZA, MTX) or oral preparations of herbal immunomodulatory medications within 8 weeks prior to randomization.
- l) Exposure to JAK inhibitors such as tofacitinib, baricitinib, filgotinib, or upadacitinib within 8 weeks prior to randomization.
- m) Intravenous (IV) immunoglobulin within 8 weeks prior to randomization or during the study.
- n) Allergen immunotherapy within 4 months of randomization.
- o) Biologics depending on the type:
 - i) Cell-depleting agents, including rituximab: within 6 months, or until the targeted population (eg, CD19+ lymphocyte counts for rituximab) returns to normal, whichever is longer

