 - ii) Biologics such as tocilizumab and anakinra within 8 weeks prior to randomization
 - iii) Other biologics: within the longer of 5 half-lives (if known) or 6 months of randomization (eg. dupilumab)
- p) Prior exposure to BTK inhibitors such as ibrutinib, acalabrutinib, or experimental drugs (eg, BMS-986166 or branebrutinib, tirabrutinib, vecabrutinib, zanibrutinib, ARQ-531, GDC-0853, or others) at any time.
- q) Prior exposure to S1PR modulators (eg, fingolimod, etrasimod, ozanimod, etc.) at any time.

- r) Use of any immunomodulator or investigational drug not listed above within the longer of 5 PK half-lives, 5 PD half-lives, or 6 months of randomization.

5) Laboratory Test and Procedural Findings

- a) The following test findings at Screening or Baseline
- i) WBC count < 3000/ μ L or > 14,000/ μ L
 - ii) ANC < the lower of: lower limit of normal (LLN) or 1500/ μ L
 - iii) ALC < 1000/ μ L
 - iv) Platelet count < 100,000/ μ L
 - v) Serum creatinine > 2 mg/dL
 - vi) Estimated glomerular filtration rate (eGFR) < 60 mL/min/1.73 m² as calculated using the Chronic Kidney Disease Epidemiology Collaboration (CKD-EPI) equation¹¹⁰:
$$\text{eGFR} = 141 \times \min(\text{Scr}/\kappa, 1)^\alpha \times \max(\text{Scr}/\kappa, 1)^{-1.209} \times 0.993^{\text{Age}} \times 1.018 [\text{if female}] \times 1.159 [\text{if black}]$$
-- where Scr is serum creatinine, κ is 0.7 for females and 0.9 for males, α is -0.329 for females and -0.411 for males, min indicates the minimum of Scr/ κ or 1, and max indicates the maximum of Scr/ κ or 1.
 - vii) AST or ALT >1.5x ULN
 - viii) Total bilirubin > 2 mg/dL (34 μ mol/L)
 - ix) Hemoglobin <10 g/dL
 - x) ECG: HR < 55 bpm; PR \geq 210 msec; QRS \geq 120 msec; QTcF >450 msec males, > 470 msec females, or any clinically significant heart conduction abnormality (eg, left bundle branch block, atrial fibrillation).
 - xi) Abnormality on posteroanterior + lateral chest radiograph, taken during the Screening period that is relevant to safe conduct of this study.
 - xii) Abnormality on optical coherence tomography (OCT) testing suggestive of macular or choroidal pathology beyond that expected for a healthy person of the participant's age.
 - xiii) Heart rate < 55 bpm or > 95 bpm at rest
 - xiv) Blood pressure > Grade 1 hypertension (> 159 mmHg systolic and > 99 mmHg diastolic) according to the 2018 European Society of Cardiology/European Society of Hypertension guidelines for the management of arterial hypertension¹¹¹

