CYP2C8 and CYP3A4 -Strong or moderate inhibitors	clopidogrel, gemfibrozil, clarithromycin, itraconazole	Prohibited during the study	5 PK half-lives or 14 days of randomization
CYP2C8 and CYP3A4 -Strong or moderate inducers	rifampin, phenytoin	Prohibited during the study	3 weeks of the randomization
CYP2C8 or P-gp Sensitive substrates with narrow therapeutic indices	Repaglinide, dabigatran, fexofenadine	Prohibited during the study (digoxin allowed under limited/urgent circumstances; see below)	5 PK half-lives or 14 days of randomization
Immunization against agents other than influenza or SARS-CoV-2	Live vaccines	Prohibited during the study	90 days before and 60 days after EOT
	Nonlive vaccines unassociated with influenza or SARS-CoV-2		30 days before and 60 days after EOT

Table 7.7.1-1: Prohibited and Restricted Medications

Type of Medication	Examples (not exhaustive)	Restriction	Required Washout
Immunization for influenza or SARS-CoV-2	Live vaccines	Prohibited during the study	90 days before and 60 days after EOT
	Nonlive vaccines for influenza or SARS-CoV-2		14 days prior to screening and 60 days after EOT
Immunosuppressants -systemic or oral preparations of herbal immunomodulatory medications	Mycophenolate-mofetil, azathioprine, methotrexate	Prohibited during the study	8 weeks prior to randomization
JAK inhibitors	Tofacitinib, baricitinib, filgotinib, and upadacitinib	Prohibited during the study	8 weeks prior to randomization
Leukotriene inhibitors	montelukast	Prohibited during the study	4 weeks prior to randomization
Monoamine Oxidase Inhibitors	Selegiline, phenelzine	Prohibited during the study	2 weeks prior to randomization
Narcotic analgesics	Oxycodone and, hydrocodone	Prohibited during the study	Not applicable
Non-narcotic analgesics	Acetaminophen	Brief courses for up to 7 days allowed	Not applicable
Phosphodiesterase Inhibitor	Apremilast, crisaborole	Prohibited during the study	3 weeks prior to randomization
Phototherapy	UVB, UVA	Prohibited during the study	4 weeks prior to randomization
S1P Receptor Modulators	Fingolimod, ozanimod, siponimod, etrasimod	Prohibited lifetime use	Not applicable
Treatments to be restricted or suspended during the study	rosiglitazone	Dose up to 4 mg can be used, monitor glucose closely	Not applicable
	torasemide	Dose up to 10 mg can be used	Not applicable

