8 DISCONTINUATION CRITERIA

8.1 Discontinuation from Study Treatment

Participants MUST discontinue investigational product (and non-investigational product at the discretion of the investigator) for any of the following reasons:

- Participant's request to stop study treatment. Participants who request to discontinue study treatment will remain in the study and must continue to be followed for protocol specified follow-up procedures. The only exception to this is when a participant specifically withdraws consent for any further contact with him/her or persons previously authorized by participant to provide this information
- Any clinical adverse event (AE), laboratory abnormality or intercurrent illness which, in the opinion of the investigator, indicates that continued participation in the study is not in the best interest of the participant
- Termination of the study by Bristol-Myers Squibb (BMS)
- Loss of ability to freely provide consent through imprisonment or involuntary incarceration for treatment of either a psychiatric or physical (eg, infectious disease) illness. (Note: Under specific circumstances and only in countries where local regulations permit, a participant who has been imprisoned may be permitted to continue as a participant. Strict conditions apply and BMS approval is required.)
- Asthma or COPD that requires systemic glucocorticoid or biologic treatment, or inhaled budesonide or equivalent at >1200 µg/day or fluticasone propionate at > 880 µg/day along with another anti-asthma/COPD drug such as a long-acting beta-agonist.
- Systemic or photo-based rescue therapy for AD ([Section 7.7.2](#)),
- Replication-competent (live) vaccine
- Grade 4 lymphopenia (ALC < 200) with repeat testing within 7 days (according to the Common Toxicity Criteria for Adverse Events [CTCAE] version 5.0)
- Elevation of ALT or AST > 5x ULN or concurrent elevations of ALT or AST > 3x ULN and bilirubin > 2x ULN
- Decline in PFT values (FEV1 and/or FVC) below 30% of the baseline values
- Diagnosis of macular edema, retinal or choroidal disease or syndrome
- Grade 2 or higher cardiac or bone marrow adverse events (with exception of ALC) according to the CTCAE version 5.0.
- Grade 3 for other system adverse events (according to the CTCAE version 5.0)
- Missed dose of ≥ 3 consecutive days or overall compliance < 85% over a period of > 30 days starting from study Day 1.

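### Exclusion 5)a)xiv, taken literally, excludes only participants above both blood-pressure limits, so isolated systolic or diastolic elevation is not excluded by the numbers

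*Combined protocol and SAP*

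**What the plan says.** Section 6.2, part 5)a), lists findings that exclude a participant at Screening or Baseline. Item xiv is "Blood pressure > Grade 1 hypertension (> 159 mmHg systolic and > 99 mmHg diastolic"), and the line continues "according to the 2018 European Society of Cardiology/European Society of Hypertension guidelines". The guideline is cited, but its rule for a reading with one high and one acceptable component is not set out.

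The other cover at entry is discretionary. Exclusion 1)a) lets the investigator exclude for an illness or unstable condition judged to raise risk substantially. Item 5)a)xv does the same for other clinically significant abnormalities. Neither names a blood-pressure value.

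Section 6.2 closes by requiring that every criterion be fully met, and Section 9 allows no waivers.

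**The concern.** Item xiv is an operative safety exclusion, and its bracket holds the only blood-pressure numbers that a site or a programmed eligibility check can apply directly. With *and* between them, someone with a very high systolic pressure and a diastolic pressure of 99 or less is not caught, and the same holds the other way round. A safety threshold that passes a large elevation in one component gives a doubtful result when it is followed exactly.

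What is at stake is who enters the trial, and whether sites in a multicentre study treat the same reading alike. One site may apply the bracket as written, while another goes to the guideline or uses its own judgement.

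**Working it through.** The plan derives no figure here, so there is none to reproduce. The check is one of logic and of the protocol's own usage.

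**Inputs.** Systolic limit 159 mmHg and diastolic limit 99 mmHg, both from Section 6.2, 5)a)xiv.

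**Rules compared.**
- Literal rule: exclude if systolic > 159 and diastolic > 99.
- Either-limit rule: exclude if systolic > 159 or diastolic > 99.

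| Systolic > 159 | Diastolic > 99 | Literal | Either-limit | Example |
|---|---|---|---|---|
| No | No | Not excluded | Not excluded | 150/90, 159/99 |
| Yes | No | Not excluded | Excluded | 185/90, 165/95, 190/99 |
| No | Yes | Not excluded | Excluded | 150/112, 150/102 |
| Yes | Yes | Excluded | Excluded | 165/102 |

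The rules differ in 2 of 4 cases, exactly those with one limit exceeded. A check of every whole-number pair with systolic 80 to 259 and diastolic 40 to 159 (180 × 120 = 21,600 pairs) found no exception.

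Size of the two main examples: 185 − 159 = 26 mmHg over on systolic; 112 − 99 = 13 mmHg over on diastolic. Under the literal rule there is no numeric ceiling on one pressure while the other stays within its limit.

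**Usage elsewhere in the protocol.**
- One of two measures is enough: "AST or ALT >1.5x ULN" (item vii of the same list) and "Decline in PFT values (FEV1 and/or FVC) below 30% of the baseline values" (Section 8.1). Exclusion 1)d)iii also joins FEV1 and FVC with *or*.
- Items i (white cells) and xiii (heart rate) write *or* as well, though there the two limits are the low and high ends of one measure, so *and* could not have been meant.
- A joint condition: "concurrent elevations of ALT or AST > 3x ULN and bilirubin > 2x ULN" (Section 8.1), where an extra word signals that both must hold. Item xiv has no such word.
- *And* as a list word: "CYP2C8 and CYP3A4 -Strong or moderate inhibitors" in Table 7.7.1-1, where exclusion 4)e) has "Use of strong or moderate inhibitors or inducers of CYP2C8 or CYP3A4"; and "or HIV-1 and -2 antibody" in exclusion 2)b).

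The two-measure items are the closest comparators. They indicate that when either value excludes, this protocol tends to say so, which supports taking *and* in item xiv at face value.

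**The case against.** The strongest reply is that the bracket only glosses a grade defined in a named guideline, so a site unsure about 185/90 knows where to look. That is fair as far as it goes, and it softens the effect. But the guideline's rule for mixed readings is not in the documents, so they cannot show that it closes the gap. If it does exclude on either component, that is a reason to make the bracket agree.

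A second reply is that discretion and monitoring cover the risk. Exclusions 1)a) and 5)a)xv do allow such a participant to be kept out. After entry, vital signs are taken hourly for six hours on Day 1 (Table 2-2, footnote b), and Section 8.1 stops treatment for cardiac events of Grade 2 or higher and for Grade 3 events in other systems. All of this stands, but discretion sets no common threshold and later monitoring does not decide eligibility.

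A third reply is that the safety weight is modest. For BMS-986166 the cardiovascular concerns described are slow heart rate, conduction delay and hypotension, and for the BTK class atrial fibrillation. Section 3.2.1.5 reports no clinically meaningful vital-sign changes in the multiple-dose study. This stands too, and it keeps the priority low.

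A reader might go further and infer that item xiv is evenly balanced between two readings. The documents do not support that. The list-word examples are weak: one is a table row label, the other can be read as the name of a test (Section 9.4.9 lists it that way), and neither joins two numeric limits. The either-limit reading remains possible because the item opens with a grade, but the wording leans towards requiring both.

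**Conclusion.** The point holds as a low-priority correction to a safety criterion. Followed literally, item xiv excludes only participants above both limits, and isolated elevation in either component is not excluded by the numbers.

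This rests on reading *and* in its ordinary sense and on no other numeric blood-pressure limit appearing in the protocol. It does not rest on any view of what the guideline says. A reader might infer that the bracket contradicts the Grade 1 label, or that participants such as the 185/90 example will in fact be enrolled. Neither follows: the grading rule is not reproduced, and the guideline reference and the investigator's judgement could each keep such a participant out.

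Two of four cases describes where the rules differ; it does not measure how often. The documents give no blood-pressure distribution, so the share of participants affected cannot be computed. Sample size, power and analyses do not change.

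**What to change.** In item 5)a)xiv, put *and/or* between the two limits: *> 159 mmHg systolic and/or > 99 mmHg diastolic*. Section 8.1 already uses that form for FEV1 and FVC. Make any eligibility check that uses the rule match. If the sponsor does mean that both limits must be exceeded, write *both* and state how isolated elevation is to be handled.

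The cost is one or two words in an amendment, an update to any such check, and possibly a few more screen failures. Section 6.4.1 allows an assessment to be repeated once during screening, with the latest value before randomization deciding, which should limit exclusions that rest on a single high reading.

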6.3 Lifestyle Restrictions

Lifestyle restrictions are listed below.

6.3.1 Meals and Dietary Restrictions

With the exception of the 8-hour fasting requirement prior to blood sample collection for safety and PK testing on Day 1 and Day 85, no meal or dietary restrictions are required for this study. A light meal/snack may be provided after the 2-hour PK sample and/or ECG collection insofar as to not interfere with obtaining either.

However, participants are advised to abstain from excessive consumption of quinine (tonic water), grapefruit and Seville oranges.

St. John's wort and herbal medications are not allowed.

6.3.2 Caffeine, Alcohol, and Tobacco

With the exception of prohibited alcohol abuse as defined by the diagnostic criteria for Drug and Alcohol Abuse defined in the DSM-5 ([Appendix 7](#)) within six months prior to randomization, there are no restrictions on caffeine, alcohol, or tobacco use for this study. However, participants who use tobacco or alcohol should be counseled for potential contraindications with non-study treatments as appropriate, and continued study participation should be based on investigator judgment.

6.3.3 Activity

The use of contraceptives during sexual activity is mandatory as stated in [Section 6.1](#).

Use of tanning beds is prohibited during the study.

6.4 Screen Failures

Screen failures are defined as participants who consent to participate in the clinical study but who are not subsequently randomized in the study/included in the analysis population. A minimal set of screen failure information is required to ensure transparent reporting of screen failure participants, to meet the Consolidated Standards of Reporting Trials (CONSORT) publishing requirements, as applicable, and to respond to queries from regulatory authorities. Minimal information includes date of consent, demography, screen failure details, eligibility criteria, and any serious AEs.

6.4.1 Retesting During Screening or Lead-In Period

Participant Re-enrollment: This study permits the re-enrollment of a participant that has discontinued the study as a pre-treatment failure (ie, participant has not been randomized / has not been treated) due to an issue that is transient. If re-enrolled, the participant must be re-consented.

Retesting of laboratory parameters and/or other assessments within any single Screening or Lead-in period will be permitted one time (in addition to any parameters that require a confirmatory value). The most current result prior to Randomization is the value by which study inclusion will be assessed, as it represents the participant's most current, clinical state.

7 TREATMENT

Study treatment is defined as any investigational treatment(s), marketed product(s), placebo or medical device intended to be administered to a study participant according to the study randomization or treatment allocation

Study treatment includes both Investigational [Medicinal] Product (IP/IMP) and Non-investigational [Medicinal] Product (Non-IP/Non-IMP) and can consist of the following:

An investigational product, also known as investigational medicinal product in some regions, is defined a pharmaceutical form of an active substance or placebo being tested or used as a reference in a clinical study, including products already with a marketing authorization but used or assembled (formulated or packaged) differently than the authorized form, or used for an unauthorized indication, or when used to gain further information about the authorized form.

Other medications used as support or escape medication for preventative, diagnostic, or therapeutic reasons, as components of the standard of care for a given diagnosis, may be considered as non-investigational products.

Table 7-1: Study Treatments for IM018005

Product Description / Class and Dosage Form	Potency	IP	Blinded or Open Label	Packaging	Storage Conditions (per label)
BMS-986166-04 capsule	0.25 mg	IP	Blinded	Bottle	Refer to the label on the container
Branebrutinib capsule (BMS-986195-01)	3 mg	IP	Blinded	Bottle	Refer to the label on the container
Placebo capsule	NA	IP	Blinded	Bottle	Refer to the label on the container

Abbreviations: IP = investigational product; NA = not applicable

7.1 Treatments Administered

The selection and timing of dose for each participant is as follows.

Table 7.1-1: Selection and Timing of Dose

Study Treatment	Unit dose strength(s) / Dosage level(s)	Dosage formulation Frequency of Administration	Route of Administration
BMS-986166	0.25 mg / 0.25 mg	QD	Oral
BMS-986166	0.25 mg / 0.50 mg	QD	Oral
BMS-986166	0.25 mg / 0.75 mg	QD	Oral
Branebrutinib	3 mg / 9 mg	QD	Oral
Placebo	NA	QD	Oral

Abbreviations: NA = not applicable; QD = once daily

Participants will be randomized to one of the following dose levels of BMS-986166 or branebrutinib or placebo in blinded fashion:

- BMS-986166 0.25 mg PO QD
 - BMS-986166 0.50 mg PO QD
 - BMS-986166 0.75 mg PO QD
 - Branebrutinib 9 mg PO QD
 - Placebo PO QD
- The first dose of double-blind study medication (BMS-986166 or branebrutinib or placebo) will be taken in the morning on Day 1 after fasting for at least 8 hours.
 - Study medication should be taken at approximately the same time each day.
 - Participants will take 3 capsules each day, one from each of 3 distinct bottle.

The actual IP taken by each participant is summarized in Table 7.1-2.

Table 7.1-2: Investigational Product: as Dispensed to Participants

Treatment Group	Double-blind Kit	Bottle A	Bottle B	Bottle C
Placebo	Each kit contains Bottle A, Bottle B, Bottle C	Placebo capsule	Placebo capsule	Placebo capsule
`166 0.25 mg QD		`166 capsule, 0.25 mg	Placebo capsule	Placebo capsule
`166 0.5 mg QD		`166 capsule, 0.25 mg	`166 capsule, 0.25 mg	Placebo capsule
`166 0.75 mg QD		`166 capsule, 0.25 mg	`166 capsule, 0.25 mg	`166 capsule, 0.25 mg
BRA 9 mg QD		BRA capsule, 3 mg	BRA capsule, 3 mg	BRA capsule, 3 mg

Abbreviations: `166 = BMS-986166-04; BRA = branebrutinib; QD = daily

Note: all capsules are identical (size 0).

In the morning on Day 1, after fasting for at least 8 hours, each participant will receive an oral dose of BMS-986166 or branebrutinib or placebo, each consisting of 3 capsules. At the time of

dosing, 240 mL of water will be administered to the participant along with his/her dose of study drug. The time of dose administration will be called “0” hour. A light meal/snack may be provided after the 2-hour PK sample and/or ECG collection insofar as to not interfere with obtaining either.

Storage of investigational product will be according to the label on the container and/or packaging.

Restrictions related to food and fluid intake are described in [Section 6.3](#).

